#### **6.4.2 Replacement rules for each analysis set**

1. Intent-to-Treat Set (ITT): all missing values of the primary endpoints will be replaced according to the MI under MAR assumption method for the primary analysis and according to the MWV, WC, LOCF and BOCF methods in order to perform four distinct sensitivity analyses. Missing values of the secondary endpoints will be replaced according to the MI under MAR assumption method.
2. Per Protocol Set (PP): no replacement of missing data is required for the primary and secondary endpoints.
3. Safety Set: no replacement of missing data is required for the safety endpoints.

## 6.5 Analysis centers

Each center conducted the clinical study under a common protocol. Consistency in study execution at each center was emphasized. The study had to be conducted in such a manner as to have a minimum of 8 ITT subjects enrolled in each of the treatment groups at each center (i.e. 16 ITT subjects enrolled overall). In the event that there are too few subjects in a treatment arm for a center, then this center's data will be combined with another center's data in order to achieve the desired minimum number of subjects per treatment arm. The combining of data across centers will be accomplished by combining data from two or more centers based on geographic and climatic similarities until the minimum number of subjects per treatment arm is achieved. The sequence of combination will be based on the total number of subjects enrolled in each center (combining lowest to 2nd lowest and so on). Combining center data to achieve sufficient subjects per treatment arm will result in the combined centers. These combined centers, as well as individual centers with sufficient subjects per treatment arm, will be referred to as "analysis centers" in the statistical analyses.

Supposing to have  $N$  geographic and climatic areas with  $M_i$  ( $i=1..N$ ) centers for each area, we can write the set of all centers as

$$\{C_{ij}\}_{i=1..N, j=1..M_i}$$

and the set of ordered centers according to the ascending number of enrolled subjects within each geographic and climatic area as

$$\{C_{ij(k)}\}_{i=1..N, k=1..M_i} \mid \forall i, m < n \Rightarrow \#(C_{ij(m)}) \leq \#(C_{ij(n)})$$

Using this notation, each geographic and climatic area  $i$  can have up to  $A_i$  ( $\forall i=1..N, A_i \leq M_i$ ) analysis centers

$$\{AC_{ij}\}_{i=1..N, j=1..A_i}$$

For example

$$\begin{aligned} AC_{i1} &= C_{ij(1)} \cup C_{ij(2)} \cup C_{ij(3)} \\ AC_{i2} &= C_{ij(4)} \cup C_{ij(5)} \\ AC_{i3} &= C_{ij(6)} \\ &\dots \\ AC_{iA_i} &= C_{ij(M_i)} \end{aligned}$$

The definition of the analysis centers will be performed before the database lock during the blind review meeting/conference.

## **6.6 Demographic, baseline and background characteristics and other study information**

Demographic, baseline and background characteristics will be reported for all the enrolled subjects and analyses will be performed according to the treatment the subjects actually received (PP and Safety) and according to the treatment they were assigned (ITT).

### **6.6.1 *Subjects' disposition***

The disposition of all subjects enrolled in the study will be listed and summarised by treatment group (CB-03-01 and Vehicle). The number and percentage of subjects completing the study, the number and percentage of withdrawals and the reasons for withdrawal will be presented ([Listing 16.2.4.1](#), [Table 14.1.1.1](#)).

### **6.6.2 *Analysis sets***

The subjects included in each analysis sets will be listed and summarised by treatment group (CB-03-01 and Vehicle) ([Listing 16.2.4.2](#), [Table 14.1.1.2](#)).

### **6.6.3 *Subjects excluded from efficacy and/or safety analysis***

All subjects excluded from the efficacy and/or safety analysis will be listed and the reasons for exclusion will be reported ([Listing 16.2.3.1](#)).

### **6.6.4 *Discontinued subjects***

All subjects who discontinued the clinical trial will be listed. Sex, age, last visit performed before discontinuation, type of discontinuation, date of premature discontinuation and primary reason for subject premature discontinuation will be reported ([Listing 16.2.1.1](#)).

### **6.6.5 *Protocol deviations***

All the protocol deviations reported during the clinical trial will be listed by subject and summarised by treatment group (CB-03-01 and Vehicle); the number and percentage of subjects for each deviation will be reported ([Listing 16.2.2.1](#), [Table 14.1.1.8](#), [Table 14.1.1.9](#)).

### **6.6.6 *Blind breaking***

In case of any blind breaking, whether the unblinding was confirmed or not and the reason for unblinding will be listed by treatment group ([Listing 16.2.2.2](#)).

### **6.6.7 *Mismatches of assigned and received IMPs***

In case of any mismatches of assigned and received IMPs, the assigned and actually received IMPs will be listed ([Listing 16.2.2.3](#)).

### **6.6.8 *Demography***

Demographic data will be listed and summarised by treatment group (CB-03-01 and Vehicle). The number and percentage of subjects in each category of categorical variables (e.g. sex) and the descriptive statistics (mean, standard deviation, CV%, minimum, median and maximum) of continuous variables (e.g. age) will be presented (Listing 16.2.4.3, Table 14.1.1.3, Table 14.1.1.4, Table 14.1.1.5).

#### **6.6.9 Inclusion/Exclusion criteria**

All the unmet inclusion/exclusion criteria will be listed and summarised by treatment group (CB-03-01 and Vehicle). The number and percentage of subjects for each skin type will be reported (Listing 16.2.4.4, Table 14.1.1.6, Table 14.1.1.7).

#### **6.6.10 Fitzpatrick Skin Type Assessment**

The Fitzpatrick skin type assessments will be listed and summarised by treatment group (CB-03-01 and Vehicle). The number and percentage of subjects for each skin type will be reported (Listing 16.2.10.1, Table 14.1.1.10, Table 14.1.1.11).

#### **6.6.11 Medical and dermatological history**

All the findings of medical history of all subjects enrolled in the study will be coded using the Medical Dictionary for Regulatory Activities (MedDRA) and listed (Listing 16.2.10.2). The version of the dictionary used for coding will be reported in the clinical study report.

The findings of medical history will be summarised by treatment group (CB-03-01 and Vehicle). The number and percentage of subjects with any findings will be presented by PT and SOC (Table 14.1.1.12).

#### **6.6.12 Dermatological examination and brief physical examination**

Whether the dermatological examination was performed or not and, if performed, the date of examination and the presence of facial acne vulgaris, hypopigmentation, hyperpigmentation and other dermatological findings on face and whether the physical examination was performed or not and, if performed, the date of examination will be listed (Listing 16.2.10.3).

#### **6.6.13 Prior and concomitant medications**

All prior and concomitant medications will be coded using the World Health Organization Drug Dictionary Enhanced (WHO DDE) and listed (Listing 16.2.10.4). The version of the dictionary used for coding will be reported in the clinical study report.

Prior and concomitant medications will be listed and summarized by treatment group (CB-03-01 and Vehicle). The number and percentage of subjects with any concomitant medication will be presented by and ATC 4th level (or the higher available ATC level if 4th level is missing) and standardised drug name (Table 14.1.1.13, Table 14.1.1.14).

#### **6.6.14 Concurrent Therapies and Procedures**

Non medication concurrent therapies and procedures will be listed ([Listing 16.2.10.5](#)) by treatment group (CB-03-01 and Vehicle).

#### **6.6.15 Photographs**

Whether photographs were taken or not and, as applicable, the reason for not collecting them or the date of collection will be listed ([Listing 16.2.10.6](#)) by treatment group (CB-03-01 and Vehicle).

#### **6.6.16 Subjects study visits**

The dates of all subjects study visits will be listed ([Listing 16.2.10.7](#)) by treatment group (CB-03-01 and Vehicle).

### **6.7 Efficacy analysis**

Subjects will be analysed according to the analysis center they will be assigned to and to the treatment they were assigned to (ITT, PP).

The original clinical center of the subjects will be used only for the the investigation of center-to-center variability.

The investigator's global assessment scores will be listed ([Listing 16.2.6.1](#)) and summarised by treatment group (CB-03-01 and Vehicle) using contingency tables ([Table 14.2.1.1](#), [Table 14.2.1.2](#)).

The proportion of subjects with at least a two-point reduction in IGA AND an IGA score of 0 (clear) or 1 (almost clear) will be summarised by treatment group (CB-03-01 and Vehicle) using contingency tables ([Table 14.2.1.3](#), [Table 14.2.1.4](#)).

The acne lesion counts will be listed by treatment group ([Listing 16.2.6.2](#)); the values of NILC and ILC and their changes from baseline will be summarised by treatment group (CB-03-01 and Vehicle) using descriptive statistics ([Table 14.2.1.5](#), [Table 14.2.1.6](#)).

#### **6.7.1 Primary efficacy analysis**

##### **6.7.1.1 Proportion of subjects in each treatment group with at least a two-point reduction in IGA compared to Baseline AND an IGA score of 0 (clear) or 1 (almost clear) at Week 12 - ITT**

A logistic regression model with treatment and analysis center as fixed effects will be used to compare the proportion of subjects in each treatment group with at least a two-point reduction in IGA AND an IGA score of 0 (clear) or 1 (almost clear) at Week 12 ( $\pi_{2p(0,1)}$ ). Subjects will be analysed according to the treatment they were assigned to (ITT) and missing data will be replaced using a multiple imputation (MI) under missing at random (MAR) assumption.

The adjusted odds ratio of the comparison of  $\pi_{2p(0,1)}$  between CB-03-01 and Vehicle and its 95% confidence interval will be derived from the regression model (Table 14.2.2.1).

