17.3.1 Efficacy Analyses

17.3.1.1 Primary Efficacy Analysis

Hypothesis tests on the primary endpoints will be conducted in hierarchical order for P1 through P3.

P1: A logistic regression model with treatment and analysis center as fixed effects will be used to compare the proportion of subjects achieving “success” in each treatment group at Week 12, where “success” is defined as an IGA score of “clear” (score=0) or “almost clear” (score=1) AND at least a two-point improvement in IGA compared to Baseline.

P2: An analysis of covariance (ANCOVA) will be used to compare the absolute change from Baseline in non-inflammatory lesion count in each treatment group at Week 12, with treatment and analysis center as fixed effects and the Baseline non-inflammatory lesion count as the covariate.

P3: An ANCOVA will be used to compare the absolute change from Baseline in inflammatory lesion count in each treatment group at Week 12, with treatment and analysis center as fixed effects and the Baseline inflammatory lesion count as the covariate.

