#### 3.1 Investigator's Global Assessment (IGA)

At every study visit, overall severity of acne using a five-point scale from 0 (clear) to 4 (severe) was assessed. This is a static morphological scale that refers to a point in time and not a comparison to Baseline. Subjects had to have an IGA score of 3 (moderate) or 4 (severe) at Baseline.

Score	Assessment	Description
0	Clear	Absence of active disease with no inflammatory or non-inflammatory lesions
1	Almost Clear	Rare non-inflammatory lesions with no more than one small inflammatory lesions
2	Mild	Some non-inflammatory lesions with no more than a few inflammatory lesions (papules/pustules only; no nodular/cystic lesions)
3	Moderate	Up to many non-inflammatory lesions and may have some inflammatory lesions but no more than one nodular/cystic lesion
4	Severe	Up to many non-inflammatory lesions and inflammatory lesions but no more than a few nodular/cystic lesions

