A post-hoc analysis of the data collected in the Phase 2 Dose Escalation Study 171-7151-201 (6) performed only for the subjects with 30-75 inflammatory lesions and 30-100 non-inflammatory lesions at baseline provided the following results for the proportion of success and the related sample size estimation.

	TEST	VEHICLE
Success	3 (12.50%)	0 (0.00%)
Failure	21 (87.50%)	22 (100.00%)

Since the number of success is zero for VEHICLE, a continuity correction (Haldane correction) was applied to each cell in the previous table in order to calculate the odds ratio:

	TEST	VEHICLE
Success	3.5 (14.00%)	0.5 (2.17%)
Failure	21.5 (86.00%)	22.5 (97.83%)

$$\text{OR}_{2p(0,1),TV} = \frac{\pi_{2p(0,1),\text{TEST}}(1 - \pi_{2p(0,1),\text{VEHICLE}})}{\pi_{2p(0,1),\text{VEHICLE}}(1 - \pi_{2p(0,1),\text{TEST}})} = 7.3256$$

$$\alpha = 0.05 \text{ two - sided}, \beta = 0.033 \Rightarrow N_{\text{TEST}} = N_{\text{VEHICLE}} = 202$$

**202 subjects per group** should be enrolled in order to have 202 subjects per group included into the ITT Set.

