### 6.4 Handling of missing data

#### 6.4.1 Methods for replacing missing data

1. Multiple imputation (MI) under missing at random (MAR) assumption: multiple imputation is a general approach to the problem of missing data that aims to allow for the uncertainty about the missing data by creating several different plausible imputed data sets and appropriately combining results obtained from each of them. Missing at random (MAR) approach assumes that any systematic difference between the missing values and the observed values can be explained by differences in observed data. The use of multiple imputation under MAR assumption provides unbiased estimations of the parameters and allows to evaluate the uncertainty of parameters' estimation due to the presence of missing data.

A Markov Chain Monte Carlo (MCMC) method that assumes multivariate normality will be used to impute all the missing values. In order to prevent a power falloff due to choosing a number of imputations too small, 10 imputations will be performed (10).

The multiple imputation procedure will be implemented by using the MI procedure of the SAS system with the following options:

- NIMPUTE=10
- SEED=1
- ROUND=0
- MINMAXITER=10000000

and the following MCMC statement:

- MCMC IMPUTE=FULL CHAIN=SINGLE INITIAL=EM (BOOTSTRAP=0.9 CONVERGE=1E-6 ITPRINT MAXITER=1000)

A unique imputation process will be performed without taking into account the treatment arm.

The imputed data sets will be then analysed with the MIANALYZE procedure of the SAS system with the following options:

- ALPHA=0.05
- EDF=number of subjects of the ITT set - number of estimated parameters (including intercept)]

Type-III analyses obtained from multiple imputations will be combined according to the method proposed by Binhuan Wang and Yixin Fang (11).

2. Missing as Worst Value (MWV): for each subject, missing values of a variable will be replaced with the worst value (failure in case of dichotomous variables or the higher value collected in the study for lesions counting) of that variable regardless of the treatment arm.

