#### **6.7.1.2 Absolute change from Baseline in NILC at Week 12 - ITT**

An analysis of covariance (ANCOVA) will be used to compare the absolute change from Baseline in NILC in each treatment group at Week 12, with treatment and analysis center as fixed effects and the Baseline NILC as covariate. Subjects will be analysed according to the treatment they were assigned to (ITT) and missing data will be replaced using a multiple imputation (MI) under missing at random (MAR) assumption.

The adjusted means difference of the comparison of NILC between CB-03-01 and Vehicle and its 95% confidence interval will be derived from the regression model (Table 14.2.2.2).

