#### **6.7.1.3 Absolute change from Baseline in ILC at Week 12 - ITT**

An ANCOVA will be used to compare the absolute change from Baseline in ILC in each treatment group at Week 12, with treatment and analysis center as fixed effects and the Baseline ILC as covariate. Subjects will be analysed according to the treatment they were assigned to (ITT) and missing data will be replaced using a multiple imputation (MI) under missing at random (MAR) assumption.

The adjusted means difference of the comparison of ILC between CB-03-01 and Vehicle and its 95% confidence interval will be derived from the regression model (Table 14.2.2.3).

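### The P1 logistic model omits Baseline IGA (3 vs 4); adding it is nearly free and slightly raises test efficiency, though it does not make the log odds ratio more precise

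*SAP*

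**What the plan says.** The protocol (17.3.1.1) and the SAP (6.7.1.1) give the same P1 model. The SAP states: "A logistic regression model with treatment and analysis center as fixed effects will be used to compare the proportion of subjects" with success. SAP 6.7.3.1.1 repeats it for the per-protocol set. The adjusted odds ratio and its 95% interval from this model are the reported P1 effect.

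The other two primary endpoints carry a baseline term. The P2 model is fitted "with treatment and analysis center as fixed effects and the Baseline NILC as covariate", and the P3 model "with treatment and analysis center as fixed effects and the Baseline ILC as covariate".

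On baseline severity, SAP 3.1 states: "Subjects had to have an IGA score of 3 (moderate) or 4 (severe) at Baseline". Every eligible subject therefore has a two-level baseline IGA. SAP 6.2.1 does allow for missing baseline assessments, as a reason for exclusion from the per-protocol set.

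Missing P1 data are multiply imputed (SAP 6.4.1), with this restriction: "A unique imputation process will be performed without taking into account the treatment arm". The SAP does not list the variables in the imputation model. Analysis centers (SAP 6.5) are sites pooled until each arm has at least 8 ITT subjects. They are fixed at the blind review, so their number is not given.

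**The concern.** Success means a Week 12 score of 0 or 1 with a drop of at least two points. From grade 3 that is a fall of two grades. From grade 4 a two-point fall ends at 2, which is not success, so three grades are needed. Baseline IGA thus sets how far each subject must move. It is already collected and takes one parameter, yet P1 is the only primary endpoint without its own baseline in the model, and no reason is given.

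P1 is also the first test in the hierarchy: if it fails, nothing after it can be claimed. Any efficiency that can be had there for nothing is worth taking.

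**Working it through.** **1. The plan's own figure.** SAP 4.3.1 uses n = (z_α/2 + z_β)² / (log OR)² × [1/(pT(1−pT)) + 1/(pV(1−pV))], with pT = 3.5/25 = 0.1400, pV = 0.5/23 = 0.0217, OR = 7.3256, α = 0.05 two-sided and β = 0.033.
- (1.960 + 1.838)² = 14.43; (log 7.3256)² = 1.991² = 3.966; bracket = 8.31 + 47.02 = 55.33.
- n = 14.43 / 3.966 × 55.33 = 201.3, rounded up to 202. This reproduces the SAP.
- With 350 per arm the same formula gives z = 1.991 / √(55.33/350) = 5.01 and power of 99.9%. At the planning odds ratio there is no power left to gain.

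That odds ratio is fragile. It rests on 3/24 against 0/22: "Since the number of success is zero for VEHICLE, a continuity correction (Haldane correction) was applied to each cell". The useful question is what happens at a smaller effect.

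**2. Effect of adding Baseline IGA.** The simulations use complete data and 2000 trials per setting, with 732 subjects at 48 sites (SAP 2.4) in blocks of 4 by site (SAP 2.6), pooled by the SAP 6.5 rule. Assumed: site sizes, five areas, site SD 0.5 on the logit scale, 15-30% grade 4, success OR 0.5-0.2 for grade 4 against grade 3, and all success rates except those at the planning OR. With about 30 centers, 30% grade 4 and grade OR 0.2:

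| Vehicle vs active | True OR | Mean z, planned | Mean z, with IGA | Change |
|---|---|---|---|---|
| 2.17% vs 14.0% | 7.33 | 4.967 | 5.029 | +1.2% |
| 5% vs 14.8% | 3.3 | 4.127 | 4.182 | +1.3% |
| 7% vs 14% | 2.16 | 2.925 | 2.968 | +1.5% |

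- Over all grade settings the gain in mean z is 0.2-1.5%. If grade does not predict success, z changes by −0.06% to +0.08%.
- Power at OR 2.16 (84-87%) changes by −0.1 to +0.5 points, within Monte Carlo error of √(0.85 × 0.15 / 2000) = 0.8 point. A separate run at an assumed OR of 2.2 gave −0.3 to +2.3 points.
- Type I error with 8% success in both arms: 5.1-5.3% planned, 5.2% with IGA.

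**3. Where the gain in z comes from.** In a further run at OR 2.16 the odds ratio moved from 2.18 to 2.25 and the standard error of its log from 0.264 to 0.270. Then z is log 2.18 / 0.264 = 2.95 against log 2.25 / 0.270 = 3.00. The estimate moves away from 1 by more than the standard error grows. At OR 7.33 the standard error rose from 0.397 to 0.403 and the odds ratio from 7.62 to 8.04.

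**4. Separation.** With 15% grade 4 there are 732 × 0.15 ≈ 110 such subjects, 55 per arm. With grade OR 0.2, their success rates are about 3.6% (active) and 0.5% (vehicle) at the planning rates, so 55 × 0.036 + 55 × 0.005 ≈ 2.3 successes are expected. The chance of none is e^−2.3 ≈ 10%. Simulation gave about 10% there and about 6% at OR 2.16; milder settings gave 0-3%.

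**5. Center intercepts.** At most 732 / 16 = 45 analysis centers are possible. With complete data, the fixed-center odds ratio exceeds the conditional (center-stratified) one by 5-12% at OR 7.33 and 2-5% at an assumed OR of 2.2 over 20-45 centers. Under the SAP 6.5 pooling rule with assumed site sizes (median about 25-32 centers) the excess is about 6-8% and 3-3.5%. With no treatment effect the ratio is 1.00.

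**6. Imputation can pull the other way.** Suppose a share m of outcomes is imputed with no arm information. Each arm's rate becomes (1−m)p + m × pooled rate. At m = 5%, 14.00% and 2.17% become 13.70% and 2.47%, and the odds ratio falls from 7.34 to 6.28; 14% and 7% become 13.8% and 7.2%, and it falls from 2.16 to 2.08. A missing share of about 2.0-2.5% (OR 7.3) or 3.5-4.3% (OR 2.16) would cancel the excess. Observed Week 4 and 8 data in the imputation would weaken this pull.

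**The case against.** The strongest case against acting is that there is little to gain. The protocol and SAP agree on the model, Type I error is sound, the power change is mostly within simulation error, and enrollment is complete, so a change means defending a departure from the protocol. All of that is true, and it is why the point is minor. It does not outweigh a consistent, if small, gain for one parameter while the data are still blinded.

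A reader might infer that adjustment makes the P1 estimate more precise, as it does for lesion counts. It does not: in logistic regression the standard error rises (step 3).

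It is also fair to object that adding IGA enlarges the fixed-center odds ratio. With 30% grade 4 and grade OR 0.2 it goes from 7.70 to 8.13 against a true 7.33, and from 2.18 to 2.25 against 2.16. Part of this is a change of target, since the odds ratio becomes conditional on IGA, and part is the many center intercepts. The conditional model with IGA gives 7.42 and 2.17, which is why it is offered as a supportive estimate.

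The separation objection stands too. The treatment term can still be estimated in that case, but a fallback has to be written down.

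**Conclusion.** Minor. Leaving Baseline IGA out of the P1 model is a missed small improvement and not an error. Adding it raises mean z by about 0.2-1.5% if grade predicts success, changes nothing of note if it does not, and is unlikely to alter the P1 decision. These sizes rest on an assumed grade 4 share, grade effect, site sizes and success rates; the documents give none of these except the planning rates.

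A reader might go further and infer that the reported P1 odds ratio will be too high because of the center intercepts. The documents do not support that. The number of analysis centers is not given, an odds ratio near 2.2 is an assumption, the excess was shown for complete data only, and the planned arm-blind imputation can pull the estimate down by a similar amount. The net direction is not established.

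**What to change.** Before database lock:

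1. In SAP 6.7.1.1 and 6.7.3.1.1, fit treatment, analysis center and Baseline IGA (3 vs 4, any ineligible lower score grouped with 3) as fixed effects. The other sensitivity and interaction analyses that repeat 6.7.1.1 follow automatically.
2. Name Baseline IGA among the imputation variables in SAP 6.4.1.
3. Keep the protocol model without IGA as a sensitivity analysis, and state in advance that it becomes the P1 model if the IGA term separates (no grade 4 successes). With imputed data, say that the same model is used in all ten data sets.
4. Declare the departure from Protocol 17.3.1.1 in SAP 1.1, which now reports no change.
5. Optional: add to Table 14.2.2.1 a supportive odds ratio and 95% interval from conditional logistic regression stratified by analysis center, with treatment and Baseline IGA, log odds ratios pooled over imputations.

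Cost: no new data and one parameter. With an assumed 30 centers the SAP 6.4.1 degrees of freedom go from 732 − 31 = 701 to 732 − 32 = 700. The standard error and the unconditional odds ratio both become slightly larger. The conditional row costs no power as a supportive estimate; used as the primary test it would lower mean z by 1.0-2.4% and power at OR 2.16 by about 0.1-1.1 points, so it should stay supportive.
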